7 STUDY PROCEDURES

This section describes visit-specific study procedures.

7.1 Pre-Screening

As part of participant outreach and recruitment strategies, study staff may pre-screen potential study participants (e.g. via telephone using an IRB approved screening script). During these interactions, study staff may explain the study to participants and ascertain elements of presumptive eligibility, to be confirmed at an on-site screening visit. If the participant is eligible based on a screening script the person's name and appointment time will be placed on the script. If the person signs consent, the telephone script will then become part of the research record. If the person does not sign consent, the form will be de-identified.

7.2 Visit 1: Screening Visit

At the Screening Visit, participants will provide written informed consent prior to study procedures. Study personnel will collect participant locator Information, demographic, and medical history information. The participants will undergo a physical examination including a visual examination of the nose and throat using a lighted instrument (otoscope). Safety labs will be obtained, and for female participants of child-bearing potential, a urine pregnancy test will be performed. A nasopharyngeal swab will be collected for SARS-CoV-2 testing per local standards. Participants who meet all eligibility criteria will be scheduled for the enrollment visit (Visit 2) within 60 days of the screening visit.

Table 1: Visit 1 Procedures		
VISIT 1: SCREENING VISIT		
Component	Procedure/Analysis	
ADMINISTRATIVE	 Written Informed Consent Informed Consent Comprehension Assign Study Number (PTID) Review Eligibility Collect Contact Information Medical History and Concomitant Medications Visit Questionnaire Provide Available Screening Results Protocol Counseling Schedule Next Study Visit, prn Participant Reimbursement 	
NASOPHARYNGEAL	SARS-CoV-2	
URINE	Pregnancy test for participants of childbearing potential	
BLOOD	 CBC with platelets ALT, AST Creatinine Total Bilirubin 	
PHYSICAL EXAM	 Full Physical Exam Vital Signs (BP) Height & Weight 	

The table below outlines the procedures to take place at the Screening visit.

7.3 Visit 2: Enrollment

Subjects who meet the inclusion and exclusion criteria following the Screening visit may schedule an Enrollment visit. This visit is to occur within 60 days of the Screening Visit.

At this visit, locator information will be updated, and eligibility reviewed. Participants will undergo a smell assessment prior to drug delivery. The Brief Smell Identification Test (BSIT) contains 12 odorants embedded on scent strips and released when scratched with a pencil tip. The BIST is a forced choice test as participants are instructed to identify an odorant even if no smell is perceived. The total olfaction score using the BSIT is defined as the number of odorants that are correctly identified.

The participant will be sequence randomized to receive either Q-GRFT nasal spray or placebo nasal spray. The clinician will administer the first dose of study product. After reviewing administration instructions, the participant will try the metered dose delivery system by delivering product into a paper towel. Participants will be asked to wait at the research trial site for one hour after product administration for observation. All participants will undergo an assessment of adverse events, targeted physical exam, blood draw, and assessment of smell approximately one-hour postnasal spray administration.

Interested participants may participate in an optional enrollment visit sampling (nasal, oropharyngeal, and nasopharyngeal) at a single timepoint between 1- and 12-hours post product administration. Participants must agree to all three sample collections to be eligible for this optional enrollment visit sampling.

VISIT 2: ENROLLMENT – PRE		
Component	Procedure/Analysis	
ADMINISTRATIVE	 Review/Confirm Eligibility Collect/Update Contact Information Visit Questionnaire Quality of Life Survey Update Medical History and Concomitant Medications Provide Available Screening Results Protocol Counseling 	
URINE	Pregnancy Test (participants of childbearing potential)	
PHYSICAL EXAM	 Targeted Physical Exam Assessment of Smell (BSIT) Vital Signs (BP) 	
BLOOD	 Q-GRFT level ADA test for Anti Q-GRFT antibodies	
NASAL	Q-GRFT level	
OROPHARYNGEAL	Q-GRFT level	
NASOPHARYNGEAL	Q-GRFT level	
STUDY PRODUCT	 Randomized to study product Study Product Provision Clinician-administered 	
1-HR POST-DOSE		
Component	Procedure/Analysis	
ADMINISTRATIVE	 Assess/Document Adverse Events Schedule Next Study Visit Participant Reimbursement 	
BLOOD	 Q-GRFT level CBC with platelets ALT, AST Creatinine Total Bilirubin 	

Table 2: Visit 2 Procedures

PHYSICAL EXAM	 Targeted Physical Exam Assessment of Smell (BSIT) Vital Signs (BP) 	
OPTIONAL SINGLE TIME POINT SAMPLES (1 – 12-hour post-dose)		
Component	Procedure/Analysis	
NASAL	Q-GRFT level	
OROPHARYNGEAL	Q-GRFT level	
NASOPHARYNGEAL	Q-GRFT level	

7.4 Visit 3 Follow-Up Visit

Visit 3 will occur the day after the enrollment visit. Every effort will be made to time the study visit for 24 hours after dosing. At this visit, a safety assessment will be performed via medical interview, targeted physical exam, and repeat blood tests. An assessment of participant smell will be performed using the BSIT. Samples (blood, nasal, oropharyngeal, and nasopharyngeal) will be collected, and an acceptability questionnaire will be administered.

VISIT 3 FOLLOW-UP VISIT	
Component	Procedure/Analysis
ADMINISTRATIVE	 Collect/Update Contact Information Visit Questionnaire Update Medical History and Concomitant Medications Protocol Counseling Assess/Document Adverse Events Schedule Next Study Visit Participant Reimbursement
ACCEPTABILITY	Acceptability Questionnaire
BLOOD	 Q-GRFT level CBC with platelets AST, ALT Creatinine Total Bilirubin
NASAL	Q-GRFT level
OROPHARYNGEAL	Q-GRFT level
NASOPHARYNGEAL	Q-GRFT level
PHYSICAL EXAM	 Targeted Physical Exam Assessment of Smell (BSIT) Vital Signs (BP)

Table 3: Visit 3 Follow-up Visit Procedures

7.5 Visit 4 [Extended Dosing; 1st week of study product provision]

Visit 4 will occur 5-49 days after Visit 3. If any of the safety labs (e.g.Hemoglobin, AST, ALT, Creatinine, bilirubin) obtained at Visit 3 are returned as Grade 2 or higher, this visit will be postponed until the abnormal lab returns to Grade 1 or Grade 0 but within the 49-day window period.

Ideally, participants will return within the week for Visit 4 but the extended window will allow for flexibility for the participant or any disruptions to visit scheduling caused by external forces, for example a spike in SARS-CoV-2 cases at the institution prompting a pause in study visits. Medical history will be updated, a targeted physical exam conducted, safety labs, blood and respiratory sampling obtained, and study product provided to the participant. After reviewing administration instructions with the participant, the first dose of the 13-day course will be self-administered under direct observation in the clinic. The participant will then self-administer product daily at home for the remainder of the dosing period. A one-week supply will be provided at Visit 4.

Participants will be provided with an administration log to record date and time of drug

administration.

Table 4:	Visit 4	Follow-up	Visit	Procedures
		i onon ap	1010	110000000000

VISIT 4 FOLLOW-UP VISIT [week one of extended dosing]				
Component	Procedure/Analysis			

ADMINISTRATIVE	 Collect/Update Contact Information Visit Questionnaire Quality of Life Survey (pre-dose) Update Medical History and Concomitant Medications Protocol Counseling Provision of Study Product (week one supply) Assess/Document Adverse Events Schedule Next Study Visit Participant Reimbursement 				
	CBC with platelets				
BLOOD					
	AOI, ALI Creatinine				
	Total Bilirubin				
URINE	 Pregnancy test (participants of childbearing potential) 				
OROPHARYNGEAL	Q-GRFT level				
NASAL	Q-GRFT level				
NASOPHARYNGEAL	Q-GRFT level				
	Targeted Physical Exam				
PHYSICAL EXAM	Assessment of Smell (BSIT)				
	Vital Signs (BP)				

Participants will be contacted in between Visit 4 and Visit 5 to assess for adverse events. This contact will be considered Visit 4a.

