7.6 Visit 5 [Extended dosing; second week of product provision)

Visit 5 will occur 7 days after Visit 4. A safety assessment will be performed via medical interview and physical exam. An assessment of smell will be performed. The second week of study product will be provided. Participants will be provided with an administration log to record date and time of drug administration.

VISIT 5 FOLLOW-UP VISIT [week two of extended dosing]				
Component	Procedure/Analysis			
ADMINISTRATIVE	 Collect/Update Contact Information Visit Questionnaire Quality of Life Survey Update Medical History and Concomitant Medications Protocol Counseling Assess/Document Adverse Events Provision of Study Product (week two supply) Schedule Next Study Visit Participant Reimbursement 			
PHYSICAL EXAM	 Targeted Physical Exam Assessment of Smell (BSIT) Vital Signs (BP) 			
BLOOD	 CBC with platelets AST, ALT Creatinine Total Bilirubin 			

Table 5: Visit 5 Follow-up Visit Procedures

Participants will be contacted in between Visit 5 and Visit 6 to assess for adverse events. This contact will be considered visit 5a.

7.7 Visit 6

Visit 6 will occur approximately 13 days after Visit 4. Every effort will be made to time the study visit for 24 hours after the last self-administered dose. At this visit, a safety assessment will be performed via medical interview, targeted physical exam, and repeat blood tests. An assessment of participant smell will be performed using the BSIT. Blood and respiratory samples will be collected. An acceptability questionnaire will be administered. Participants have the option to have a rectal swab collected.

VISIT & FULLOW-UP VISIT [24 nours after last self-administered dose]				
Component	Procedure/Analysis			
ADMINISTRATIVE	 Collect/Update Contact Information Visit Questionnaire Quality of Life Survey Update Medical History and Concomitant Medications Protocol Counseling Assess/Document Adverse Events Schedule Next Study Visit Participant Reimbursement Q-GRFT level 			
BLOOD	 ADA test for Anti Q-GRFT antibodies CBC with platelets AST, ALT Creatinine Total Bilirubin 			
ACCEPTABILITY	Acceptability Questionnaire			
URINE	Pregnancy test (participants of childbearing potential)			
NASAL	Q-GRFT level			
OROPHARYNGEAL	Q-GRFT level			
NASOPHARYNGEAL	Q-GRFT level			
RECTAL (optional)	Q-GRFT level			
PHYSICAL EXAM	 Targeted Physical Exam Assessment of Smell (BSIT) Vital Signs (BP) 			

T	able	6:	Visit	6	Follow	-up	Visit	Ρ	rocedu	ires
		17							la a coma	- 44 -

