7.8 Visit 7

Visit 7 will occur 28 days after Visit 4. At this visit, a final safety assessment will be performed via medical interview, targeted physical exam, and repeat blood tests. An assessment of participant smell will be performed using the BSIT. Samples (blood and respiratory) will be collected. An acceptability questionnaire will be administered.

VISIT 7 FOLLOW-UP VISIT						
Component	Procedure/Analysis					
ADMINISTRATIVE	Visit Questionnaire					
	Quality of Life Survey					
	Update Medical History and Concomitant Medications					
	Assess/Document Adverse Events					
	Participant Reimbursement					
ACCEPTABILITY	Acceptability Questionnaire					
BLOOD	Q-GRFT level					
	 ADA test for Anti Q-GRFT antibodies 					
	CBC with platelets					
	AST, ALT					
	Creatinine					
	Total Bilirubin					
URINE	 Pregnancy test (participants of childbearing potential) 					
NASAL	Q-GRFT level					
OROPHARYNGEAL	Q-GRFT level					
NASOPHARYNGEAL	Q-GRFT level					
PHYSICAL EXAM	Targeted Physical Exam					
	Assessment of Taste and Smell (BSIT)Vital Signs (BP)					

Table 7: Visit 7 Follow-up Visit Procedures

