7.9 Visit Window Periods

While every attempt will be made to evaluate the participant on the protocol specified date, the following visit windows are allowable

Visit 3: 24 hours after first dose (24-48 hours)

- Visit 4: 5-49 days after Visit 3
- Visit 5: 7 days after Visit 4 (5-7 days)

Visit 6: 13 days after Visit 4 (12-13 days) *

Visit 7: 28 days after Visit 4 (25-32 days)

*If scheduling requires that the participant be seen 12 days after Visit 4 rather than 13 days after, participants will be instructed to hold the final home dose and present to the clinic the next day

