7.11 Interim Visits

Interim visits may be performed at any time during the study (and study procedures repeated as clinically indicated), for the following or other reasons:

• In between screening and enrollment or Visits 3 and 4 if laboratory tests need to be repeated due to out of range values

- For administrative reasons, e.g., a participant may have questions for study staff, or may need to re-schedule a follow-up visit.
- In response to AEs. When interim contacts or visits are completed in response to participant reports of AEs, study staff will assess the reported event clinically and provide or refer the participant to appropriate medical care.
- In the event of laboratory processing issues (i.e., lost or inadequate sample)
- For other reasons at participant request.

Details of the interim visit will be recorded in the chart notes.

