9.6.3 Analysis Cohort

The intent-to-treat cohort (ITT) will be defined as those who were enrolled. It will be used for analyses of baseline characteristics, protocol deviations and violations, and trial conduct. The evaluable cohort (Eval) is a subset of ITT participants. Evaluable participants will be defined as participants who complete Visit 6 procedures.

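### A first-dose lab toxicity that keeps a participant from reaching Visit 4 also makes that participant non-evaluable, and section 9.6.3 names no analysis set that would keep the event in the primary safety proportion

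*Combined protocol and SAP*

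**What the plan says.** **Visit schedule.** Section 7.5 sets the start of the 13-day course: "Visit 4 will occur 5-49 days after Visit 3". A Grade 2 or higher safety lab from Visit 3 changes this: "this visit will be postponed until the abnormal lab returns to Grade 1 or Grade 0 but within the 49-day window period". Each later visit is dated from Visit 4: "Visit 5 will occur 7 days after Visit 4" (7.6), "Visit 6 will occur approximately 13 days after Visit 4" (7.7) and "Visit 7 will occur 28 days after Visit 4" (7.8). Section 7.9 gives windows around the same anchor.

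**Follow-up outside the schedule.** Section 7.11 permits interim visits, including "In between screening and enrollment or Visits 3 and 4 if laboratory tests need to be repeated due to out of range values". Section 8.3 follows clinically significant occurrences until they resolve or stabilize over four weeks. Section 8.6 calls for reasonable effort at a final evaluation of those who withdraw or are withdrawn.

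**Endpoint.** Under 8.3 an abnormal laboratory finding is an adverse event, graded by the DAIDS table and classed as related or not related. Section 9.3.1 makes any related Grade 2 or higher event a primary event, with no visit restriction. Section 9.6.2 counts each participant once.

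**Analysis sets.** Section 9.6.3 defines two. ITT is everyone enrolled, and its listed uses are baseline characteristics, deviations and violations, and trial conduct. For the other, "Evaluable participants will be defined as participants who complete Visit 6 procedures". No set is assigned to the primary endpoint. Accrual aims at about 45 evaluable participants (9.2), and the randomization scheme holds 48 places (9.5).

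**The concern.** A lab abnormality that appears within 24 to 48 hours of the first dose and persists for weeks is one form of the systemic toxicity that the primary objective is meant to detect. The participant who has it cannot start the second period while it persists. Without Visit 4 there is no Visit 6, and without Visit 6 the participant is not evaluable. If the primary proportion is computed in the evaluable cohort, the toxicity has removed itself from the safety result. Accrual towards a target of evaluable participants could then fill the place with someone who tolerated the first dose. The bias runs in one direction, towards a more favourable safety estimate, and with about 30 people on Q-GRFT a single case is visible in the upper bound.

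**Working it through.** **1. Trace the participant.**
- Visit 3 falls 24 to 48 hours after dose 1 (7.9). Suppose a safety lab there is Grade 2 or higher.
- Visit 4 is postponed. The window closes 49 days after Visit 3, which is at most 2 + 49 = 51 days after dose 1.
- If the lab is still Grade 2 or higher at that point, 7.5 states no outcome.
- Visits 5, 6 and 7 are Visit 4 plus 7, 13 and 28 days, so none has a date. The last scheduled visit was Visit 3.
- Interim visits (7.11) are optional and untimed. Section 8.3 depends on the occurrence being clinically significant. Section 8.6 applies to withdrawn participants, a status that no section gives to this case.
- Section 8.4 fixes an outcome only for related Grade 4 events and related SAEs, and a review for related Grade 3 events. A persistent Grade 2 lab gets neither.

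Pregnancy is a useful comparison. Sections 7.10 and 10.1 say that product stops, follow-up continues and the participant is not excluded from analysis. Nothing equivalent is written for the unresolved lab.

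**2. Trace the event into the analysis.** If judged related, the lab is a primary event (8.3, 9.3.1), counted once (9.6.2). Whether it enters the proportion depends on the set. The participant belongs to ITT, whose listed uses do not include safety, and cannot belong to the evaluable cohort. Section 9.2 uses 30 both as the Q-GRFT share of 45 evaluable (45 × 2/3) and as the number enrolled in that arm, so it does not settle the matter.

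**3. Reproduce the plan's figures.** Table 9 gives two-sided 95% exact (Clopper-Pearson) intervals for n = 30. The upper bound for x events in n is the 0.975 quantile of Beta(x + 1, n − x). For x = 0 this reduces to 1 − 0.025^(1/n).
- 0/30: 1 − 0.025^(1/30) = 11.57%; the plan gives 11.6%.
- 1/30: Beta(2, 29) gives 17.22%; the plan gives 17.2%.
- 2/30: Beta(3, 28) gives 22.07%; the plan gives 22.1%.

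All 16 rows of Table 9 match to 0.1 point.

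**4. Size of one such case.** Assumption: one Q-GRFT participant has a related Grade 2 or higher lab after dose 1 that does not resolve within the window, and a replacement is recruited to the same arm. Then 31 people on Q-GRFT have been dosed and 30 are evaluable. The 48 places allow up to 48 × 2/3 = 32 on Q-GRFT, so 31 is attainable.

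| Other related events | Evaluable set: upper bound | All dosed: upper bound | Difference |
|---|---|---|---|
| 0 | 0/30: 11.57% | 1/31: 16.70% | 5.1 points |
| 2 | 2/30: 22.07% | 3/31: 25.75% | 3.7 points |

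Without replacement and with no other events, the comparison is 0/29 (11.94%) against 1/30 (17.22%), a difference of 5.3 points.

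**The case against.** The strongest reply is that much of the machinery exists. Several stronger readings are tempting, and the documents do not support them.

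- **That the event has no scoring rule.** It has one: sections 8.3, 9.3.1 and 9.6.2 together score a related Grade 2 or higher lab. What is missing is the set of participants over whom the proportion is taken.
- **That the participant is lost to follow-up.** The postponement rule itself implies repeat labs, 7.11 provides for them, and 8.3 and 8.6 add further routes. This follow-up is weaker than a dated visit, but it exists.
- **That 7.5 contradicts itself.** The Protocol Summary starts the second period only if the first dose is safe and acceptable. The ordinary reading is therefore that an unresolved lab means the second period does not begin. The gap is an unstated status, not two incompatible rules.
- **That one case defeats a claim to rule out rates above 22.1%.** Section 9.2 makes that statement conditional on event rates similar to the 5.5% it cites. At 3/31 (9.7%) the condition is not met, so the statement would not apply.
- **That an anti-drug antibody sample is missing.** That objective is exploratory and concerns multiple treatments (3.5), so a single-dose participant falls outside it.
- **That the retention figure gives a frequency.** The figure above 95% in 5.3 describes retention in other phase 1 studies. It says nothing about labs that stay at Grade 2 or higher for 49 days.

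It is also fair to say that the unnamed set affects every participant who misses Visit 6. That stands, and the remedy below covers them all. The path in 7.5 deserves separate mention because there the exclusion is caused by the safety outcome itself.

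**Conclusion.** The point holds in a limited form. Section 7.5 leaves one safety path without a stated status, later scheduled visits depend on Visit 4, and 9.6.3 does not say that a dosed participant who misses Visit 6 stays in the primary proportion. If the evaluable cohort is used, a first-dose event is removed by the rule it triggered. One such event lowers the Q-GRFT upper bound by 5.1 points when there are no other events, and by 3.7 points when there are two.

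This rests on four assumptions: that the evaluable cohort would be used for the primary endpoint, which the plan does not say; that the lab is judged related, although the trigger in 7.5 applies whatever the cause; that the participant is replaced, which is inferred from the evaluable target and the 48 places and not stated; and that such a case occurs at all. The documents give no rate, and the path is probably rare. It should still be settled in advance, because safety is the primary endpoint and the error favours the product.

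**What to change.** **Section 9.6.3.** Name all randomized participants who received at least one dose as the set for the primary safety endpoint, whether or not Visit 4 or Visit 6 took place. Count their related Grade 2 or higher events in the numerator, keep them in the denominator, and show those who received a single dose separately. Keep the evaluable cohort as a supportive set and for endpoints measured at Visit 6.

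**Sections 7.5 to 7.9, 8.3, 8.6 and 9.6.3.** Reconcile these so that the status and safety follow-up of a participant whose lab is unresolved when the window closes are stated. What that status and follow-up should be is a clinical decision for the sponsor; no visit timing or clinical rule is proposed here.

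**Cost.** A few sentences of wording. The reported upper bound may be slightly less favourable, and the denominator may differ from the 30 used in Table 9.

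### No adverse event contact is scheduled between Visits 3 and 4, so when Visit 4 is delayed, events starting after Visit 3 rest on self-report or on recall of up to 49 days

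*Combined protocol and SAP*

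**What the plan says.** After the first, clinician-administered dose, adverse events are assessed at about one hour (section 7.3) and again at Visit 3, which falls 24-48 hours after dosing (sections 7.4 and 7.9). The next scheduled assessment is Visit 4, where the 13-day course begins. Section 7.9 gives its window: "Visit 4: 5-49 days after Visit 3". Section 7.5 states the intention: "Ideally, participants will return within the week for Visit 4". The rest of the window is there for flexibility and for outside disruption. A Grade 2 or higher safety laboratory result at Visit 3 can also lengthen the gap: "this visit will be postponed until the abnormal lab returns to Grade 1 or Grade 0 but within the 49-day window period".

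Two contacts are added between visits. Section 7.5 provides the first (Visit 4a): "Participants will be contacted in between Visit 4 and Visit 5 to assess for adverse events". Section 7.6 provides the second (Visit 5a): "Participants will be contacted in between Visit 5 and Visit 6 to assess for adverse events". The Protocol Summary and Appendix 1 list these two and no others.

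Outside scheduled assessments, participants are told how to report events to the site (section 8.3), and interim visits are allowed, including between Visits 3 and 4 to repeat laboratory tests (section 7.11). The primary endpoint is the proportion of participants with a related Grade 2 or higher event, with no restriction by dosing period (section 9.3.1).

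**The concern.** The protocol adds a solicited contact inside intervals of about a week, yet schedules none inside an interval that may be several times longer. It gives no reason for the difference.

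This bears on the primary endpoint because of how events are graded. Section 8.3 expects most events to fall under the generic row of the toxicity table. There, Grade 1 and Grade 2 are separated by how far symptoms interfered with ordinary activities and whether intervention was indicated. The first of these rests mainly on the participant's account, and judging relatedness needs a reliable onset date. Both become harder to establish as time passes. No symptom diary is described. The only participant log starts at Visit 4 and records when doses were taken.

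The Protocol Summary makes the second dosing period conditional on the first dose being safe and acceptable. An event that starts after Visit 3 and is not volunteered would first be asked about at the visit where that second period starts. Length of recall would also differ between participants according to when Visit 4 happened to fall.

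**Working it through.** No analysis figure in the plan is in dispute here. The check is of the visit windows.

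**Inputs (section 7.9)**
- Visit 3: 1-2 days after dose 1.
- Visit 4: 5-49 days after Visit 3.
- Visit 5: 7 days after Visit 4 (5-7).
- Visit 6: 13 days after Visit 4 (12-13).
- Visit 7: 28 days after Visit 4 (25-32).

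**Intervals between scheduled visits**
- Visit 3 to Visit 4: 5-49 days, ideally about a week. No contact.
- Dose 1 to Visit 4: from 1 + 5 = 6 days to 2 + 49 = 51 days.
- Visit 4 to Visit 5: 5-7 days. Contact 4a.
- Visit 5 to Visit 6: nominally 13 − 7 = 6 days; at the limits from 12 − 7 = 5 to 13 − 5 = 8 days. Contact 5a.

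At its maximum, the Visit 3-4 interval is 49 / 7 = 7 times the longest Visit 4-5 interval, which does have a contact. At the intended timing of about a week, the two are alike.

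**How likely is a long gap?** The documents give no distribution for the timing of Visit 4. Section 4.6 expects participation of 6-8 weeks including screening, that is 42-56 days. Take off 28 days for Visit 4 to Visit 7 and 1 day for Visit 2 to Visit 3:
- 42 − 29 = 13 days
- 56 − 29 = 27 days

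So 13-27 days are left for screening and the Visit 3-4 gap together. A full 49-day gap would give 1 + 49 + 28 = 78 days before any screening time, well beyond the expected 56. The long gap is therefore permitted, but it is not the expected course.

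**Which events are affected?**
- Onset up to Visit 3: actively assessed at 1 hour or at 24-48 hours. Not affected.
- Onset after Visit 3, Visit 4 at about a week: recall of about a week. Little affected.
- Onset after Visit 3, Visit 4 delayed: self-report, or recall of up to 49 days at Visit 4. Affected.

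**Effect of a weekly contact from day 7 after Visit 3.** The longest stretch without a solicited enquiry falls from 49 days to about 7. If Visit 4 falls d days after Visit 3, the number of calls is the number of multiples of 7 that are below d:
- d = 7: none
- d = 20: two (days 7 and 14)
- d = 49: six (days 7, 14, 21, 28, 35 and 42)

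**The case against.** The strongest defence is that the contacts follow exposure, not interval length. Contacts 4a and 5a cover unsupervised daily dosing at home, whereas Visits 3 to 4 is an off-drug period after one supervised dose. Section 2.5 reports an intranasal terminal half-life of 15.8-18.8 hours in rabbits, and an event that appears weeks after one dose is less likely to be judged related. This is a reasonable logic and it stands as an explanation, although the protocol does not state it. It does not exclude delayed effects, immune effects among them, and such events would count if judged related.

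It is also fair that participants can report events themselves and that those with abnormal Visit 3 laboratory results may be seen at interim visits. However, self-report and interim visits are equally available during daily dosing, where the protocol still added contacts. Section 7.11 also does not require an adverse event enquiry at a visit made to repeat laboratory tests.

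A reader might infer several stronger things that the documents do not support:
- *That first-dose events in general are collected by long recall.* They are not, because the 1-hour and 24-48 hour assessments cover the acute period.
- *That 49 days is the design.* It is the outer limit of a window whose stated aim is about a week.
- *That events are sought immediately before re-exposure.* Table 4 puts the assessment at the same visit as the first dose of the course but does not say which comes first. Only the quality of life survey is marked as pre-dose.
- *That the cost can be read from Table 9, as the upper limit of 17.2% at 1/30 against 11.6% at 0/30.* That contrast follows from missing any event for any reason and does not show that this gap loses one.

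**Conclusion.** The point holds as a minor gap in ascertainment, not as an error. Events that start after Visit 3 in participants whose Visit 4 is delayed depend on self-report or on recall of up to 49 days, although they count toward the primary endpoint. In participants seen at about a week there is little to gain.

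The number of events lost or misgraded cannot be estimated from the documents. They give neither the distribution of Visit 4 timing nor any figure for recall loss. The conclusion assumes only that some participants will use the longer window, which section 7.5 foresees, and that severity and onset are recalled less well as time passes. The sample size of 45 and the intervals in Table 9 are unaffected. The point is worth acting on because the remedy is an existing procedure applied to a few more participants.

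**What to change.** In sections 7.4 and 7.5 and in Appendix 1, extend the contact already used for 4a and 5a to any participant whose Visit 4 has not taken place by about 7 days after Visit 3. Repeat it about weekly until Visit 4, and record the findings in the same way as for 4a and 5a.

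The cost is protocol wording, a few short calls by existing staff and a slight burden on the participants concerned. It is none for those seen on time and at most six calls for someone who uses the whole window. Visit windows, dosing, sample size and analysis do not change.
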